2.2 Study Rationale

Commercially available Devil's Claw products may contain material from *H. procumbens* and *Harpagophytum zeyheri*, and both species may vary in their pro- and anti-inflammatory constituents; this has undoubtedly contributed to the lack of agreement between published reports of efficacy of such products.²¹⁻²⁵ The anti-inflammatory and analgesic properties of *H. procumbens* have been ascribed to inhibition of eicosanoid and nitric oxide (NO) biosynthesis, by altering expression and inhibition of cyclooxygenases (COX1, 2) and lipoxygenases (LOX) and nitric oxide synthase (iNOS), and to altered expression of pro- and anti-inflammatory cytokines and other mediators (recently reviewed).^{23,24} Harpagoside, 8-p-coumarylharpagide and related metabolites have been implicated as primary anti-inflammatory effectors.^{22-24,26}

For these studies, we will use botanically verified *H. procumbens* plant material and an extraction procedure comparable to WS1531 extract used in the human clinical trial reported by Chrubasik and colleagues²⁷ and the in vivo and ex vivo studies reported by Loew et al.¹ In the former study, extract WS1531 extract was compared with placebo in a randomized, double blind study of 197 patients with chronic susceptibility to back pain. At four weeks, three pain-free patients occurred in the placebo group, six in the group receiving extract containing 50mg harpagoside/day, and ten in the group receiving extract with 100mg harpagoside/day. This significant

dose-dependent pain relief was explored pharmacologically¹ where basal and A23187-induced synthesis of cysteinyl-leukotrienes (Cys-LT) was determined *ex vivo* to be dependent upon the content of harpagoside and the absence of pro-inflammatory components, as detailed in U.S. Patent 6,280,737 B1. This effect was supported by *in vivo* analyses, in which three subjects received, in a crossover fashion, 600mg, 1200 mg and 1800mg extract resulted in a statistically significant decrease (~58%) in Cys-LT levels in blood at 8hrs after treatment.

We have based our sample size on previous research published by Loew and colleagues¹ in which six healthy adult males received a single 150mg harpagoside dose through consumption of 600mg *Harpagophytum* extract HF 8858. The C_{max} value was reached within 1.3 hours following dosing and was calculated as 32.2 ng/mL; the half-life of this dose level was 5.6 hours. Given our plan to compare pharmacokinetic parameters between participants who are dosed with enteric versus non-enteric coated capsules, we doubled the sample size used by Loew and colleagues in order to do this comparison. We will collect complete data from 12 participants.

The PK Study will use HP extract with a daily harpagoside dose (100mg) that is equivalent to the dosing used in previous clinical studies that have demonstrated beneficial effects and been shown to be safe.^{3,27} The study will provide data that can confirm the bioavailability and pharmacokinetic properties of harpagoside and 8-p-coumarylharpagide following a single dose administration. Oral administration of the study product was selected based on previous clinical research and based on the administration route that would be used in clinical practice.

Previous research indicates that risks of taking *H. procumbens* extracts are limited. Devil's Claw supplements are widely prescribed in Europe and available in the United States in grocery stores, health food stores, and pharmacies. Previous research using dose levels in the range of 50-100mg harpagoside daily dose has shown it to be at least as well tolerated as more traditional pain medication (e.g., nonsteroidal anti-inflammatory drugs)^{8,9} and allergies have been rare.

We have established screening criteria to address any possible risks by excluding people with conditions that might be contraindicated. We will monitor possible side effects and adverse events throughout study participation, and participants will be given a phone number to contact study staff and/or the investigators to report side effects or adverse events, if needed. We will follow NIH guidelines for reporting adverse events to the Data Safety Monitoring Board (DSMB) and IRB. Any problems needing medical attention will immediately be triaged by [name] and when appropriate, referred to the participant's personal physician or other health care providers.

Other risks of participating in the study are minimal and include providing samples for clinical tests, having an electrocardiogram (ECG), and the inconvenience of completing questionnaires. The blood draws and ECG will be done following standard clinical guidelines to ensure no greater risk than what is expected with routine medical care. Study staff will be trained and will follow GCP and HIPAA guidelines in order to prevent any breach of participants' confidentiality and privacy

as a result of contacts with study staff.

3. STUDY DESIGN

Study Design - A one-dose randomized design will be used to measure bioavailability and pharmacokinetic properties of the *H. procumbens* study product, an aqueous extract enriched in harpagoside from which pro-inflammatory mediators have been removed by precipitation with ethanol, as described in U.S. Patent 6,280,737 B1 (HP extract). Dosing level for this study will be extract containing 100mg harpagoside, previously shown to be safe.^{2,3} Level of product markers will be measured for 24 hours following a single dose of HP extract, with blood collections taken at timed intervals.

Primary Outcomes – pharmacokinetic metrics:

C_{\max} (ng/mL) – first maximal concentration,

t_{\max} (h) – time to reach the C_{\max} ,

AUC (0-t) (ng/mL) – Area under the curve, and

Terminal $t_{1/2}$ (h) – terminal half-life.

Study Population - Adults with knee osteoarthritis (n = 12). Equal numbers of participants will be randomly assigned to receive study product in either enteric or non-enteric coated capsules.

Study Location - Participants will be recruited from MU Healthcare clinics that treat patients diagnosed with knee osteoarthritis. Participants will be treated at the University of Missouri Health Sciences Clinical Research Center (CRC). A letter of support from the Medical Director of the CRC is provided in the Appendix

Duration of Enrollment Period and Follow-up – Enrollment should be completed within 2 months after the final protocol is approved by the NIH, IRB and FDA. Each person enrolled in the study will be followed throughout the PK testing session and for the 24 hour period following the end of the testing session blood draw schedule.

Intervention and Administration - The study product will be packaged in either enteric or non-enteric capsules by [name], Pharm D, (MU-IDS Pharmacist). Participants will be randomly assigned to receive HP extract in either capsule type. At the PK testing session, all participants will receive capsules to deliver an oral dose of HP extract which provides 100mg of harpagoside.

Randomization, Blinding, and Stratification – Participants will be randomized to receive HP extract in either enteric coated or non-enteric coated capsules. Assignment to study group will be conducted double-blind. A pilot study indicated participants will not be able to distinguish between enteric and non-enteric capsules.

Other Protocol Specific Details - Analysis of all serum and urine samples will be processed using standard protocols following good clinical practices. Samples to measure study product markers will be processed at the University of Missouri (MU) and will be supervised by [name] (PI). Samples to measure safety endpoints

(complete blood count [CBC], basic metabolic panel [BMP], and liver function test [LFT]) will be processed by CLIA certified laboratories.

4. SELECTION AND ENROLLMENT OF PARTICIPANTS

4.1 Inclusion Criteria

To be eligible to participate, patients must meet all of the following inclusion criteria:

- adult (at least 18 years of age);
- diagnosed with knee osteoarthritis (OA);
- body mass index (BMI) of less than 40;
- willing to use only the *H. procumbens* (Devil's Claw) study product (HP extract) during study participation;
- able to use tramadol or Tylenol as a rescue pain medication during participation in the study;
- willing and able to monitor blood glucose levels if diabetic;
- willing to abstain from caffeine-containing drinks and food before participation in the study;
- able to read and understand English, and have the cognitive capacity to give consent; and,
- willing to abstain from use of the following during participation in the study: prescription and over-the-counter non-steroidal anti-inflammatory medications, (e.g., aspirin, ibuprofen, Advil, Motrin, Nuprin, Naproxen, etc.); any dietary supplements (St. John's Wort, etc.); and, grapefruit and/or products containing it.

4.2 Exclusion Criteria

Patients who have any of the following diagnoses or conditions will be excluded from participating:

- cardiovascular disease, previous myocardial infarction, stent, CABG, arrhythmia, high or low blood pressure;
- recurrent stomach upset, or gastric or duodenal ulcers;
- gallstones or gall bladder disease (cholelithiasis);
- liver or kidney disease; high alcohol use (more than two drinks per day on a regular basis);
- Coumadin or anti-platelet drug use;
- at risk for respiratory depression, history of seizures, or taking drugs that reduce the seizure threshold or may increase the risk for development of serotonin syndrome;
- pregnant or breast feeding, or intention to become pregnant during the study;
- pronounced allergies, or known allergy to *H. procumbens* or corn starch;
- have had an injection to treat OA within the past three months;
- currently taking NSAIDs, unless they are willing to stop for a 1-week wash-out period;
- currently on a SSRI but are poorly stabilized, or have evidence of suicidal ideation and/or suicide attempts in the past year; and,

- reported use during the 7 days prior to study drug administration of: prescription medicines, or over-the-counter medications; non-steroidal anti-inflammatory medications (e.g., NSAIDs); dietary supplements; grapefruit and/or its juice products; or products containing St. John's Wort.

4.3 Study Enrollment Procedures

The study team will work with MU Healthcare physicians to ensure that patients with qualifying diagnosis of knee osteoarthritis are identified and approached about participating in the study. Electronic medical records for potentially eligible patients will be reviewed for recorded information relevant to inclusion and exclusion criteria. A screening log will be maintained to track the patients who have been screened for eligibility, approached, and scheduled for a screening session; each individual will be assigned a screening identification (SID) number. The screening log will be used to document reasons for ineligibility and to record reason for non-participation for possibly eligible patients who decline to participate. These data will be collected in a manner to meet CONSORT guidelines.

Written informed consent (approved by the IRB) will be obtained at the screening session. The study staff will ensure that the participant is given full and adequate oral and written information about the nature, purpose, and possible risk and benefit of the study. Participants will also be notified that they are free to discontinue from the study at any time. The participant will be given the opportunity to ask questions and allowed time to consider the information provided. The participant's signed and dated informed consent will be obtained before conducting any study specific procedure. The investigator will store the original, signed Participant Informed Consent Form and a copy will be given to the participant.

A Case Report Form (CRF) will be used to record the consenting and screening session procedures including determination of eligibility based on analysis and interpretation of laboratory, physical examination, and electrocardiogram (ECG) measurements. After eligibility is determined, patients will be contacted and the PK testing session will be scheduled.

Randomized assignment into enteric or non-enteric capsule study group will occur at the beginning of the PK testing session. All study staff who have direct contact with study participants and/or are involved in data collection or analysis will be blinded as to randomization assignment. Knowledge of random assignment will remain blinded until all preliminary data reviews and quality checks are completed.

The randomization procedures and assignment list will be the responsibility of [name], Dept of Health Management and Informatics, and member of the DSMB. [name] will have no direct involvement with the study participants, data collection, or statistical analysis of the study data.

Product capsules (i.e., enteric and non-enteric) will be labeled with a product code number; [name] will be the only person with the master list that links the product code number to the type of capsule. [name] will generate a participant list that identifies the product code associated with each participant identification (PID) number; this product/participant code match will be based on the randomization

process. Study staff who work with participants and study data will only know the match of participant and product code numbers and will not know the study product material encapsulation type.

5. STUDY INTERVENTIONS

5.1 Interventions, Administration, and Duration

The intervention to be tested in this study is oral doses of HP extract packaged in capsules prepared under GMP with extract containing approximately 25mg of harpagoside, without or with enteric coating. Comparison of enteric and non-enteric formulations is warranted by reports the anti-inflammatory and analgesic activity of HP extracts, and purified harpagoside, are sensitive to gastric acid.²⁸⁻³⁰ A dose will consist of sufficient capsules to achieve consumption of 100mg harpagoside daily.

H. procumbens supplements are widely used in Europe and are widely-available in the United States in grocery stores, health food stores, and pharmacies. Previous research using dose levels in the range of 50-100mg harpagoside daily dose has shown it to be at least as well tolerated as more traditional pain medication (e.g., nonsteroidal anti-inflammatory drugs)^{8,9} and allergies have been rare.

Screening criteria address any possible risks by excluding people with conditions that might be contraindicated. We will monitor possible side effects and adverse events during the PK testing session and at each post PK testing session contact. In addition, participants will be given a phone number to contact study staff and/or the investigators to report side effects or adverse events that occur following the testing session. Any problems needing medical attention will immediately be triaged by [name] and when appropriate, referred to the participant's personal physician or other health care providers. Diagnostic laboratory tests will be ordered as specified by the study physician.

Potential side effects of *H. procumbens* supplements include mild gastrointestinal symptoms such as diarrhea, nausea, vomiting, abdominal pain; headaches; ringing in the ears; loss of appetite; and, loss of taste. It may also be related to allergic skin reactions, menstrual problems, and changes in blood pressure.⁴¹ These were reported in less than 10% of people who took it in previous research; no serious adverse events were reported.³ These side effects may be treated with an appropriate medication determined by [name] or the subject's personal physician.

5.2 Handling of Study Interventions

Aqueous-ethanolic extract of dried, milled secondary tubers of botanically verified *H. procumbens* as described in U. S. Patent 6,280,737 B1³¹ were obtained from Parceval Herbal Pharmaceuticals, LLC, South Africa (Appendix II). Sufficient product for all planned studies have been obtained as a single batch. The product complies with the FDA Guidance for Industry-Botanical Drug Products and NCCIH Natural Product Integrity Policy, and with RSA biodiversity regulations, and has received an open IND by the FDA, which must be renewed upon approval of this protocol. The content of harpagoside has been determined by HPLC-MS to be the same as that when the

FDA provided the open IND. Since that time, more extensive toxicology studies in rats have been performed and published.⁴³

Encapsulated study product will be prepared at the MU-IDS Pharmacy. Study product will be kept at room temperature in secure storage cabinets that are accessible only to authorized staff.

The dose of study product for the PK Study will be labeled with the appropriate participant identification (PID) number based on a list that links product code number to participant identification number. At the PK testing session, participants will be given one daily dose of study product. Any unused study product will be stored in the secured project storage cabinet until the completion of study data collection.

Study product accountability records will be maintained at the University of Missouri and will document: (1) the processing of the study product and packaging it with appropriate product code numbers; and, (2) the labeling of study product with participant identification number, based on the master list that documents the assignment of participant identification number for each product code.

5.3 Concomitant Interventions

5.3.1 Allowed Interventions

Participants will be allowed to use tramadol or Tylenol as a rescue medication for pain relief during the PK study data collection period; the prescription and dosing recommendations for the use of tramadol will be provided to the participant by his/her own physician. Participants will be asked to record the dates and times when they took tramadol, and the dose that was taken. This information will be provided to study staff at the follow-up contact.

5.3.2 Required Interventions

There are no required interventions in addition to the single dose of study product that each participant will receive.

5.3.3 Prohibited Interventions

Participants must agree to not use the following classes of medications while on study: medications prescribed to treat any of the exclusionary diagnoses or conditions; Coumadin or anti-platelet drug treatment; non-steroidal anti-inflammatory drugs; changes in SSRI treatment due to change in status; prescription and over-the-counter medications and dietary supplements; grapefruit and/or its products; and, St. John's Wort.

5.4 Adherence Assessment

Adherence will be documented through the CRF that will record the time of dosing. No additional dosing will be involved, and participants will not be responsible for any dosing.

6. STUDY PROCEDURES

6.1 Schedule of Evaluations

Assessment	Screening: Visit (2 – 14 days Before Testing Session)	PK Testing Session – Visit 1 (Time 0)	Follow-up - Visit 2 (24 hr)	Follow- up: Phone Contact (36 hr)
Informed Consent Form	X			
Demographics	X			
Medical History	X			
Current Medications	X	X		
Vital Signs	X	X	X	
General Physical Examination	X			
Electrocardiogram (ECG)	X		X	
Laboratory Values (CBC, CMP, LFT)	X		X	
Randomization		X		
Receive Daily Dose of Study Product		X		
Study Product Markers		X	X	
Measures of Side Effects		X	X	
Report of Adverse Events		X	X	X
Patient Reimbursement	\$50	\$125	\$50	

6.2 Description of Evaluations

6.2.1 Screening Evaluation

The Screening Evaluation session to determine whether the patient is eligible to participate in the PK Study will occur from 2 to 14 days before the PK testing session. The Screening session will include the informed consent procedure and screening activities to ensure eligibility (described below).

Consenting Procedure

Prior to participants' participation in the study, written informed consent for the study, including screening and study procedures, will be obtained from each participant. CRC project staff or [name] will ensure that the participant is given full and adequate oral and written information about the nature, purpose, possible risk and benefit of the study. The participant's signed and dated informed consent will be obtained before conducting any study specific procedures. The CRC will store the original, signed Participant Informed Consent Form and a copy will be given to the participant.

Screening

Only volunteers who consent and pass all screening assessments will be scheduled for a PK testing session. Study participation will begin within 14 days of the Screening Evaluation session. At the screening session, the individual's SID number will be used to label all study data collected at the Screening session.

Following the completion of the informed consent procedures during the Screening session, a brief survey will be completed before other screening procedures are conducted. The survey will include items to record demographic information needed to describe the study sample (e.g., age, gender, race and ethnicity) and items to record contact information (e.g., address, phone number / email address).

The following eligibility screening evaluations will be completed.

- Medical history interview – Medical history will be collected via interviews. Participants will be asked about all previous diagnoses, allergies, procedures, and treatments to verify relevant inclusion/exclusion criteria (Section 4).
- Current medication use – Participants will provide a listing of all medications (prescription and over-the-counter) they are currently taking.. Anyone who reports using medications listed in Section 4.2 Exclusion Criteria will be asked to stop use of the product for 14 days before the PK testing session.
- Vital signs – The following vital signs will be recorded to verify they are within normal ranges: heart rate, blood pressure, respiration rate.
- General physical examination – A general physical examination will be conducted.
- Electrocardiogram (ECG) – Standard 12-lead ECGs will be performed at the Screening and 24-hour follow-up sessions. The site study physician will review

the recording and verify that the participant has a normal ECG.

- Laboratory values – Blood samples will be obtained for CBC, BMP, LFT and HCG (pregnancy) for baseline product marker assays. The study physician will review the CBC, BMP, LFT and HCG (pregnancy) results to verify eligibility.

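### The medication-stop request in Protocol 6.2.1, and the washout rule in 6.2.2, do not separate drugs that 4.2 excludes outright from products that can be washed out; the 14 days in 6.2.1 is twice the 7 days used elsewhere

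*Protocol*

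**What the plan says.** Protocol 4.2 deals with medication in two ways.

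- **Outright exclusions, with no time limit or waiver.** One bullet is "Coumadin or anti-platelet drug use". Another covers people "taking drugs that reduce the seizure threshold or may increase the risk for development of serotonin syndrome".
- **Time-limited criteria.** One bullet reads "currently taking NSAIDs, unless they are willing to stop for a 1-week wash-out period". The last bullet excludes "reported use during the 7 days prior to study drug administration of: prescription medicines, or over-the-counter medications", and goes on to NSAIDs, dietary supplements, grapefruit products and St. John's Wort.

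Two later sections act on that list. In the screening medication interview, 6.2.1 states: "Anyone who reports using medications listed in Section 4.2 Exclusion Criteria will be asked to stop use of the product for 14 days", the 14 days being those before the PK session. At Visit 1, 6.2.2 has anyone reporting use of any 4.2 product since screening rebooked with a 7-day washout. Neither sentence names a subset of 4.2, and neither mentions the prescriber.

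On timing, 6.2.1 says that screening "will occur from 2 to 14 days before the PK testing session". Section 4.3 requires that "signed and dated informed consent will be obtained before conducting any study specific procedure". On who may enter, 4.1 foresees diabetic participants by asking that they be "willing and able to monitor blood glucose levels if diabetic".

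**The concern.** The stop request is tied to the whole of 4.2, but 4.2 mixes permanent disqualifiers with products that only need to clear. Followed as written, a person on an anticoagulant or anti-platelet drug is asked to stop it, although under 4.2 that drug means the person should not enter at all. Because the look-back bullet names prescription medicines without limit, the request also reaches any other prescribed drug, including one the person needs daily.

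The length is a second, smaller matter. Section 6.2.1 asks for 14 days where 4.2 and 6.2.2 use 7, and 14 days is also the far end of the screening window.

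At stake are participant safety and consistent handling of the same reported drug in a study of 12. No PK parameter, group comparison or sample-size statement depends on this.

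**Working it through.** **Scope: the sections side by side**

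| Product reported | 4.2 | 6.2.1 (screening) | 6.2.2 (Visit 1) |
|---|---|---|---|
| Coumadin, anti-platelet drug | Excluded, no time limit | Asked to stop, 14 days | Rebooked, 7-day washout |
| Drug lowering seizure threshold or raising serotonin-syndrome risk | Excluded, no time limit | Asked to stop, 14 days | Rebooked, 7-day washout |
| NSAID | Admitted after a 1-week stop | Asked to stop, 14 days | Rebooked, 7-day washout |
| Other prescription or over-the-counter medicine, supplement, grapefruit, St. John's Wort | Excluded if used in the 7 days before dosing | Asked to stop if it is a medication, 14 days | Rebooked, 7-day washout |

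The first two rows show the mismatch: 4.2 disqualifies, while 6.2.1 and 6.2.2 prescribe the same action as for the washable rows. In the last row the action agrees in kind with 4.2, but for prescribed drugs nothing says who decides that stopping is acceptable.

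**Order of events at screening.** The stop request is part of the medication interview. Under 6.2.2 the study physician's eligibility judgement comes after all screening procedures. That judgement can prevent dosing, but nothing makes the stop request wait for it.

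**The diabetic example.** Section 4.1 anticipates diabetics but mentions only glucose monitoring. Assume that such a person takes a prescribed glucose-lowering drug. It falls under the prescription-medicines item in 4.2, so 6.2.1 as worded asks the person to stop it for 14 days.

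**Length**

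Inputs:
- screening-to-testing window, days 2 to 14 (6.2.1);
- stop length, 14 days (6.2.1) or 7 days (both time-limited bullets of 4.2, and 6.2.2).

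Seven days is therefore the length in 3 of the 4 places that state one.

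Assumption: the stop starts at screening (day 0). The request responds to what is reported there, and 4.3 puts consent before any study-specific procedure.

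- Permitted days: 14 − 2 + 1 = 13.
- A stop of L days fits a session on day d when d ≥ L.
- L = 14: only day 14 fits, so 1 of 13 (7.7%).
- L = 7: days 7 to 14 fit, 14 − 7 + 1 = 8, so 8 of 13 (61.5%).
- Extra drug-free time asked by 6.2.1: 14 − 7 = 7 days.

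These are counts of calendar days, not of participants. The protocol gives no figure for how many of the 12 would report a listed drug.

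**The case against.** The strongest reply is that dosing is well guarded. Section 4.3 has medical records checked against the criteria before screening. Section 4.2 also excludes cardiovascular disease, stents, arrhythmia and a history of seizures, which removes many people likely to take the excluded drugs. Section 6.2.1 schedules only those who pass screening, and the study physician judges eligibility. This stands. A reader might infer from 6.2.1 and 6.2.2 that the protocol would take a Coumadin user off the drug and then dose that person. The documents do not support that: 6.2.1 only asks for a stop, and scheduling is separately conditional. What the safeguards leave untouched is the request itself, made in the interview and not limited to washable products.

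A second reply is that silence about the prescriber is not an instruction to bypass the prescriber. That is fair. The point is only that a rule reaching any prescribed drug should say who must agree.

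Third, a reader might take 14 against 7 days as a contradiction, or the 14-day stop as impossible. It is neither. Fourteen days satisfies a 7-day requirement, and a day-14 booking meets 4.2, 6.2.1 and the window together. Someone who had already stopped before screening is less constrained still.

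Fourth, it would be too strong to say that only NSAIDs may be washed out under 4.2. The 7-day look-back is itself time-limited and so implies a washout for the products it lists.

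**Conclusion.** The concern holds in limited form and should be fixed. The instructions in 6.2.1 and 6.2.2 are drawn too widely: they give one action for drugs that 4.2 excludes outright and for products that 4.2 lets clear. The stop request in 6.2.1 literally covers any prescribed drug, for twice the time that 4.2 needs. Existing safeguards should prevent dosing of people on the excluded drugs; they do not restrict the request.

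The 14-day length leaves 1 of 13 permitted days, against 8 of 13 for 7 days, assuming that the stop begins at screening. That is tight, not unworkable. The diabetic example assumes a drug-treated participant. The number of people affected is unknown, and the documents give no ground for inferring any effect on the PK results.

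**What to change.** In 6.2.1 and 6.2.2:

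1. Limit the stop and reschedule instruction to NSAIDs, dietary supplements, grapefruit, St. John's Wort and non-essential over-the-counter products.
2. State that the drugs 4.2 excludes outright disqualify the person.
3. State that no prescribed drug is stopped for the study unless the study physician and the prescriber agree, and that otherwise the person is not enrolled.
4. Change 14 to 7 days in 6.2.1, and book anyone who needs a washout at least 7 days after screening.

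The 7-day look-back in 4.2 can stay as it is.

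The cost is protocol wording, plus one small substantive choice: shortening the requested stop to the length already used in 4.2 and 6.2.2. No extra participants are needed. The downside is that some people on prescribed drugs may not be enrolled; the protocol gives no figure for how many.

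Two optional clarifications could be made in the same edit, though the point does not rest on them. Section 6.2.2 could say whether a rescheduled session may fall later than 14 days after screening. Section 5.3.3 could refer to the rescue-medication allowance in 5.3.1.
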